4. SCHEDULE OF ASSESSMENTS

Table 1 Schedule of Assessments for Neu-2591-PTHS

| Period | Screen Baselin 4 to 6 v | ie ^a | Baseline | seline Treatment Period | | | | | | | | | | | | | Follow- up ^b |
|--|-------------------------------|--|----------|----------------------------------|---------------------|--------------------------|--|------|---------------------|--------------------------|--|------|--|------|--------------------------|------------------|--|
| | -4 to - | Visit 1 | 0 | 1 | 2 | 3 | 4 | 5 | 6 | 7 | 8 | 9 | 10 | 11 | 12 | 13/ | 15 |
| Visit Week | 6 | +2 wks | | | | | | | | | | | | | | EOT ^b | |
| Visit Number | 1 | 2 | 3 | 4 | 5 | 6 | 7 | 8 | 9 | 10 | 11 | 12 | 13 | 14 | 15 | 16 | 17 |
| Visit window (days) | ±2ª | ±2a,c | ±la | ±l | ±2 | ±l | ±l | ±1 | ±2 | ±l | ±l | ±l | ±1 | ±1 | ±1 | -3 | +4 |
| Type of Visit | Clinic ^d | Remote and In- Home ^{e,f} | Clinicd | Remote and In- Home e,f | Clinic ^d | In- Home ^t | Remote and In- Home ^{e,f} | home | Clinic ^d | In- Home ^f | Remote and In- Home ^{e,f} | 1000 | Remote and In- Home ^{e,f} | Home | In- Home ^f | Clinic | Remote and In- Home ^{e,f} |
| Informed consent (mandatory) | X | , | | | | | | | | | | | | | | | |
| Consent for reuse of leftover Biomarker and PK samples (optional) | X | | | | | | | | | | | | | | | | |
| Inclusion/exclusion criteria | X | | X | | | | | | | | | | | | | | |
| Medical history | X | X | X | | | | | | | | į | | | | | 66 | |
| Confirm documented PTHS diagnosis and genotype | x | | | | | | | | | | | | | | | | |
| PTHS history and exam | X | | | | | | | | | | | | | | | | |
| Confirm comorbid psychiatric disorders by DSM-5 | X | | | | | | | | | | | | | | | 16 | |
| Rapid SARS-CoV-2 test | X | | X | | | | | | | | | | | | | x | |
| Autism Mental Status Exam | X | | | | | | | | | | | | | | | X | |
| Recent clinical history | | | | X | X | | X | | X | | X | | X | | | X | X |

Clinical Trial Protocol Neu-2591-PTHS-001 Version 3.0 October 30, 2023

| Period | Screening/ Baseline ^a 4 to 6 weeks | | Baseline | realine Treatment Period | | | | | | | | | | | | | |
|---|---|--|----------|----------------------------------|--------|-------------|--|------|--------|--------------------------|--|------|--|--|--------------------------|------------------|---|
| Accesses of entires. | -4 to - | Visit 1 | 0 | 1 | 2 | 3 | 4 | 5 | 6 | 7 | 8 | 9 | 10 | 11 | 12 | 13/ | 15 |
| Visit Week | 6 | +2 wks | | | | | | | | | | | | | | EOT ^b | |
| Visit Number | 1 | 2 | 3 | 4 | 5 | 6 | 7 | 8 | 9 | 10 | 11 | 12 | 13 | 14 | 15 | 16 | 17 |
| Visit window (days) | ±2ª | ±2ª,c | ±la | ±l | ±2 | ±l | ±1 | ±1 | ±2 | ±l | ±l | ±l | ±1 | ±1 | ±1 | -3 | +4 |
| Type of Visit | Clinic | Remote and In- Home ^{e,f} | | Remote and In- Home e,f | Clinic | In- Home | Remote and In- Home ^{e,f} | home | Clinic | and the same of the same | Remote and In- Home ^{e,f} | Home | Remote and In- Home ^{e,f} | The state of the s | In- Home ^f | | Remote and In- Home ^{e,} |
| Physical examination ^g | X | | X | | X | | X^h | | X | | X^h | | X^h | | | X | X^h |
| Targeted Physical Exam ^{f,g} | | N | | N | | N | N | N | | N | N | N | N | N | N | 3 | N |
| Neurological examination | X | | X | | X | | Xh | | X | | X ^h | | X ^h | | | X | X ^h |
| Ophthalmic examination ⁱ | X | | | | | | | | | | | | | | | X | * |
| Vital signs | X | N | X | N | X | N | N | N | X | N | N | N | N | N | N | X | N |
| Height/length | X | | X | | | | | | | | | | | | | X | |
| Weight | X | N | X | N | X | N | N | N | X | N | N | N | N | N | N | X | N |
| Review for AEs/SAEs | S S | | | X, N | X | N | X, N | N | X | N | X, N | N | X, N | N | N | X | X, N |
| Caregiver Diaryk | X | X | X | X, N | X | N | X | N | X | N | X | N | X | N | N | X | X, N |
| IMP administration ^c | S | | X | 3 | | | | | Т | wice da | ily | 100 | | | | 100 | |
| Review dosing compliance documentation in diary ¹ | | | | X, N | Х | N | X, N | N | X | N | X, N | N | X, N | N | N | X | |
| 12-lead ECG | X | | X | 3 3 | X | | | | X | | | 3 8 | | | | X | N |
| CBC with differential | X | | X | | X | | N | | X | | N | | N | | | X | N |
| Coagulation ^m | X | | X | 3 | X | | N | | X | | N | 3 2 | N | | | X | N |
| Comprehensive metabolic panel ⁿ | X | | X | N | X | N | N | N | X | N | N | N | N | N | N | X | N |
| Urinalysis ^o | X | | X | N | X | N | N | N | X | N | N | N | N | N | N | X | N |
| Urine screen for drugs of abuse ^o | X | | | | | | | | | | | | | | | 3 | |

Clinical Trial Protocol Neu-2591-PTHS-001 Version 3.0 October 30, 2023

| Period | Screen Baselin 4 to 6 v | ie ^a | Baseline | aseline Treatment Period | | | | | | | | | | | | | |
|--|--|--------------------------------|----------------|--------------------------|-------|-------------------|--------------|-----------|--|----------------|--------------------------------|-----------|--------------|-----------|-------------------|------------------|-------------------------------|
| 2000000 S 49000 10014 | | Visit 1 | | 1 | 2 | 3 | 4 | 5 | 6 | 7 | 8 | 9 | 10 | 11 | 12 | 13/ | 15 |
| Visit Week | 6 | +2 wks | | | | | | | | | | | | | | EOT ^b | |
| Visit Number | 1 ±2ª | 2 ±2a,c | 3 | 4 | 5 | 6 | 7 | 8 | 9 | 10 | 11 | 12 | 13 | 14 | 15 | 16 | 17 |
| Visit window (days) | 100 to 10 | Remote | ±1a Clinicd | ±1 Remote | ±2 | ±1 In- | ±1 Remote | ±1 In- | ±2 Clinic ^d | ±1 In- | ±1 Remote | ±1 In- | ±1 Remote | ±1 In- | ±1 In- | -3 | +4 Remote |
| Type of Visit | Cimic | and In- Home ^{e,f} | | and In- Home e,f | Cinic | Home ^f | | home | A STATE OF THE STA | and the second | and In- Home ^{e,f} | Home | | Home | Home ^f | | and In- Home ^{e,} |
| TSH, Free T3, Free T4 | X | | | | | | | | | | | | | | | X | |
| HbA1c | X | | | 2 | | | | | | | | 20 2 | | | | X | 0 |
| Serum pregnancy test ^p | X | | | | | | | | X | | | | | | | X | |
| Blood samples for PKq | | | | | X | | | | X | | | | | | i – | X | |
| Blood sample for biomarkers ^r | X | | X | | | | | | | | | | | | | X | |
| Stool sample for microbiome | X | | X | | | | | | | | | | | | | X | |
| CGI-I | 2 | | | | | | | | X | | | | | | | X | X |
| CGI-S | X | | X | | | | | | X | | | | | | 1 | X | X |
| Stanford-Binet Intelligence Scales version 5 (SB5) or Bayley Scales of Infant Development ver 4 ^r | Х | | | | | | | | | | | | | | | Х | |
| MB-CDI | | | X | | | | | | | | | | | | | X | |
| ORCA | | | X | | | | | | | | | | | | | X | |
| Caregiver Top 3 Concerns | X | X | X | | | | | | X | | | | | | | X | X |
| ABC-2 | X | X | X | 8 | | | | | X | | | | | | | X | X |
| BPI-SF | 00 | | X | 8 | | | | | | | | 2 | | | | X | |
| Caregiver Global Impression of Change | | | | | | | | | | | | | | | | X | |
| QI-Disability | 3 | | X | Ğ İ | | | | | | | R | 3 | | | | X | 3 4 |

Clinical Trial Protocol Neu-2591-PTHS-001 Version 3.0 October 30, 2023

| Period | Screening/ Baseline ^a 4 to 6 weeks | | Baseline | Treatment Period | | | | | | | | | | | Follow- up ^b | | |
|--|---|--|----------|----------------------------------|---|--------------------------------|--|------|---------------------|-----------------------|--|------|--|------|----------------------------|-----------------------------------|--|
| reriod | | Visit 1 | 0 | 1 | 2 | 2 | 4 | 5 | 6 | 7 | 8 | 9 | 10 | 11 | 12 | 13/ | 15 |
| Visit Week | 6 | +2 wks | U | 1 | _ | 3 | * | 3 | u . | I. | 0 | 9 | 10 | 11 | 12 | EOT ^b | 13 |
| Visit Number | 1 | 2 | 3 | 4 | 5 | 6 | 7 | 8 | 9 | 10 | 11 | 12 | 13 | 14 | 15 | 16 | 17 |
| Visit window (days) | ±2ª | ±2ª,c | ±1ª | ±l | ±2 | ±1 | ±1 | ±1 | ±2 | ±1 | ±1 | ±l | ±1 | ±1 | ±1 | -3 | +4 |
| Type of Visit | Clinic | Remote and In- Home ^{e,f} | | Remote and In- Home e,f | 100000000000000000000000000000000000000 | and the first the first to the | Remote and In- Home ^{e,f} | home | Clinic ^d | and the second second | Remote and In- Home ^{e,f} | Home | Remote and In- Home ^{e,f} | Home | In- Home ^f | A POST AT LOCATION AND ADDRESS OF | Remote and In- Home ^{e,f} |
| ICND-Overall quality of life rating | | | X | | | | | | | | | | | | | X | |
| CSHQ | X | X | X | | | | | | X | | | 3 8 | | | | X | X |
| Vineland Adaptive Behavior Scales-3 | | | X | | | | | | | | | | | | | X | |
| GIHO | X | X | X | | | | | | X | | | | | | | X | X |
| Modified two-minute walk test | X | | X | | | | | | | | | | | | | X | |
| Study Exit Form | * | 1 1 | | | | | | | | | | | | | | 3. | X ⁵ |

X = Conducted by site personnel or caregiver as applicable

N = Conducted by visiting nurse

Abbreviations: ABC-2 = Aberrant Behavior Checklist-2; AE = adverse event; BPI-SF = Behavior Problems Inventory-Short Form; CBC = Complete Blood Count; CGI-I = Clinical Global Impression Scale-Improvement; CGI-S = Clinical Global Impression Scale-Severity; CMP = Comprehensive Metabolic Panel; CSHQ = Child Sleep Habits Questionnaire; DSM-5 = Diagnostic and Statistical Manual of Mental Disorders, Fifth Edition; ECG = electrocardiogram; EOT = end of treatment; GIHQ = GI Health Questionnaire; ICND = Impact of Childhood Neurological Disability; IMP = Investigational Medicinal Product; MB-CDI = MacArthur-Bates Communicative Development Inventory; ORCA = Observer-Reported Communication Assessment; PK = pharmacokinetic; PTHS = Pitt-Hopkins syndrome; QI-Disability = Quality of Life Inventory-Disability, SAE = serious adverse events; SB5 = Stanford Binet Intelligence Scales ver 5; T3 = triiodothyronine; T4 = thyroxine; TSH = thyroid stimulating hormone.

^a No assessments can be conducted until after informed consent has been given by the caregiver or legally authorized representative. Training for the caregivers on all caregiver completed assessments must be done before the caregiver/rater may complete the assessments. The Screening/Baseline period will be conducted over 4 to 6 weeks. The second visit during the Screening period (Visit 2) should be conducted 2 weeks ± 1 day after the Screening visit (Visit 1). The participant will then remain in Screening for an additional 2 to 4 weeks. The caregiver

Clinical Trial Protocol Neu-2591-PTHS-001 Version 3.0 October 30, 2023

diary must be completed daily during the entire Screening/Baseline period whether it is 4 weeks or 6 weeks. The Screening visit (Visit 1) and Baseline visit (Visit 3) may be conducted over three consecutive days. It is preferrable that ECGs, safety labs and biomarker sample collection are conducted on the same day. All assessments must be completed within the window for the visit (visit day \pm 2 days). For Visit 3, all assessments must be completed before administration of the IMP.

- ^b The End of Treatment visit is conducted when the participant is still on IMP treatment. For early termination, in addition to study completers, participants who have received IMP for longer than 2 weeks and discontinue prematurely any time after Visit 5 should return to the investigational site for final safety and efficacy assessments as scheduled for the EOT visit (Visit 16) and complete the study exit form.
- ^c At Visit 3, the first dose of IMP will be administered in the clinic after all Baseline assessments are completed, or, if the Investigator judges that it is too late in the day, on the following day. The participant should be monitored for at least three hours post first dose. If the first dose is administered the day following Baseline, vital signs (except height) should be collected before the dose is administered. Day 1 of dosing is defined by the date when the first dose is taken. At the Baseline visit, the site will dispense an adequate supply of IMP for dispensing by the caregiver at home. Dosing at the end of Baseline counts as Day 1 whether one or two doses are given. Dosing may not exceed 91 days including Day 1, and all efficacy assessments for the EOT visit must be completed on or before Day 91 of treatment.
- ^d A clinic visit is preferred but an off-site visit may be conducted for a scheduled in-clinic visit in extenuating circumstances due to the COVID-19 health crisis. All requests for off-site visit assessments due to extenuating circumstances must be approved in advance by the Sponsor or Medical Monitor. The in-clinic visits may be conducted over three consecutive days. All assessments including caregiver-completed assessments must be done within the window for the visit.
- ^e This is a combined remote and in-person nurse visit. The remote visit is conducted by the site via telemedicine or video facilities as appropriate. Any caregiver-completed assessments should be completed the same day of the visit or no earlier than the day before the visit (except the Caregiver Diary which is completed daily) and reviewed by the Investigator. A modified version of the physical and neurological exam will be done at the remote visits based on the guidance documents provided to the Investigator. At the Week 4, the site should confirm with the caregiver that the child has started the new dose if they were approved for dose titration. These combination remote/in-home visits will be conducted simultaneously whenever possible, or they will ideally be conducted on the same day. If that is not possible, the telemedicine visit and the nurse visit may be conducted over two consecutive days. A combined remote visit may be conducted in-clinic by the study staff if agreed upon by the Investigator and the caregiver. See Section 9.1 and Section 9.2.

fin-home visits will be conducted by a visiting nurse. At every nurse visit, the nurse will collect urine, vital signs including weight, and blood samples for a comprehensive metabolic panel (CMP). The nurse will also conduct a targeted physical exam assessing general appearance, abdominal/CVA tenderness, and edema. A suprapubic exam (bladder palpation) to assess for urinary retention may be performed. The visiting nurse will also review the dosing diary, query oral intake, and do a review of tolerability. Blood samples for CBC with differential, and coagulation will be collected at Weeks 4, 8, 10 and Week 15 (indicated by "N" in the Schedule of Assessments). At the post-treatment follow-up visit at Week 15, the visiting nurse will also collect ECG, in addition to the above assessments. At Week 7, the site will also have a phone call with the caregiver to confirm that the child has started the new dose if they were approved for dose titration. The site will confirm the visiting nurse has

Clinical Trial Protocol Neu-2591-PTHS-001 Version 3.0 October 30, 2023

been informed so the dosing schedule can be reviewed with the family during the in-home visit. A nurse-only in-home visit may be conducted inclinic by the study staff if agreed upon by the Investigator and the caregiver. See Section 9.1 and 9.2.

^g The in-clinic physical exam will include an abdominal exam and an assessment of CVA. A suprapubic exam (bladder palpation) to assess for urinary retention may be performed. General awareness will be captured as part of the neurological exam. For in-home nursing visits, the nurse will do a Targeted Physical exam assessing general appearance (e.g., alertness), an abdominal/CVA, and edema. A suprapubic exam (bladder palpation) to assess for urinary retention may be performed.

^h A modified version of the neurological and physical exam will be done for the remote visit based on the guidance documents provided to the Investigator.

^j The visiting nurse will query any changes in tolerability during the in-home visit. Any changes will be noted and provided to the Investigator. The Investigator will also query changes in tolerability and note any changes in the remote assessment. The Investigator is responsible for determining and reporting any changes that qualify as Adverse Events.

^k The caregiver fills out the diary daily from the first day of screening through two weeks after the EOT Visit. X denotes review of the Caregiver Diary including the daily summary log, medication log, non-medicinal treatments log, seizure log and new/changes in symptoms log. All visits: The Investigator (or appropriately credentialed designee) is responsible for reviewing for ALL visits. In-home visits: At the in-home nurse visit, the nurse will review the Caregiver Diary to flag and check any issues that could be reported as AEs. The nurse will notify the site about any urgent issues the day of the visit and note anything else in the source documents. The nurse does not sign the diary. The source documents and the diary will be sent to the site. The Investigator (or appropriately credentialed designee) will review the diary and source documents collected at the in-home visit.

Note: There are two rows for Caregiver Diary review procedures (to emphasize the importance of thorough and complete dosing documentation): this row (Caregiver Diary) denotes that the caregiver fills out the diary daily and a designated clinician reviews it for safety/tolerability; a second row (Review dosing compliance documentation in diary, see footnote "l") is intended to ensure that the caregiver is administering IMP/documenting dose properly in the Caregiver Diary.

¹ The daily dosing log in the Caregiver Diary will be reviewed at all post-baseline visits through EOT. If any doses are missed or mis-dosed, this should be queried with the caregiver and appropriate feedback given to the family. This feedback should be documented in the source documents. At the in-home nurse visit, the nurse will review the caregiver diary to check any issues and provide feedback to the family at the visit. The nurse will notify the site about any urgent issues the day of the visit and note anything else in the source documents. The nurse does not sign the daily dosing log/summary page. The source documents and the diary will be sent to the site. The Investigator (or appropriately credentialed delegee) will review the diary and source documents collected at the in-home visit.

^m Coagulation includes prothrombin time, activated partial thromboplastin (aPTT), and international normalized ratio (INR).

Clinical Trial Protocol Neu-2591-PTHS-001 Version 3.0 October 30, 2023

ⁿ A Comprehensive Metabolic Panel will be assessed every post-enrollment visit (see Section 9.5.2). If abnormal findings are observed on renal or liver function tests, additional tests as is clinically indicated may be conducted as described in Sections 9.5.2.1 and 9.5.2.3).

^o Both urinalysis and a urine screen for drugs of abuse will be evaluated at Screening (See Section 9.5.2).

^p For female participants who have reached menarche.

^q See Table 2 and Table 3 for PK blood collection times.

^rThe Bayley is done for participants who cannot attain a basal score on SB5 or for whom the SB5 is developmentally inappropriate.

^s The study exit form should also be completed if the participant terminates the study early.

Table 2 Pharmacokinetic Blood Sampling Schedule (Participants Ages 7 to 17 Years Old)

| Week | Visit No. | Treatment | Timing of Sample (relative to start of dosing) ^a | Sample Time Point | |
|------|-----------|------------------|---|----------------------|--|
| 2 | 5 | | Pre dose (-120 to -15 minutes) ^b | 1 | |
| | | | 1-3 hours post dose ^c | 2 | |
| | | | 4-7 hours post dose ^c | 3 | |
| 6 | 9 | Mid-treatment | Pre dose (-120 to -15 minutes) b | 4 | |
| | | | 1-3 hours post dose ^c | 5 | |
| | | | 4-7 hours post dose ^c | 6 | |
| 13 | 16 | End of Treatment | Pre dose (-120 to -15 minutes) ^b | 7 | |
| | | | 1-3 hours post dose ^c | 8 | |
| | | | 4-7 hours post dose ^c | 9 | |

^a All post-dose windows are determined from the first dose of the visit (morning dose) and all PK samples must be collected before the second dose (PM dose).

^b Pre dose counts as both T0 and 12 hours post dose from previous evening (near trough). The previous evening's dose should be taken in the evening as late as possible, preferably before bedtime.

^c Post-dose sample collection can be +/- 15 minutes of the target time and must be at least 30 minutes from the previous sample (samples can be no closer than 30 minutes apart). The actual collection time must be recorded.

Table 3 Pharmacokinetic Blood Sampling Schedule (Subects Ages 3 to <7 Years Old)

| Week | Visit No. | Treatment | Collection Window | Timing of Sample (relative to start of dosing) ^a | Sample Time Point | Comment | |
|------|-----------|------------------|----------------------|--|----------------------|---|--|
| 2 | 5 | | | Pre dose (-120 to -15 minutes) ^b | 1 | | |
| | | | A | 1-3 hour post dose ^c | 2 | Sample 2 can be taken at | |
| | | | OR | OR | | either collection window A or B ^d | |
| | | | В | 4-7 hours post dose ^c | | | |
| 6 | 9 | Mid-treatment | | Pre dose (-120 to -15 minutes) b | 3 | | |
| | | | A | 1-3 hours post dose ^c | 4 | Sample 4 can be taken at | |
| | | | OR | OR | | either collection window A or B ^d | |
| | | | В | 4-7 hours post dose ^c | | | |
| 13 | 16 | End of Treatment | | Pre dose (-120 to -15 minutes) ^b | 5 | | |
| | | | A | 1-3 hours post dose ^c | 6 | Sample 6 can be taken at either collection window A or B ^d | |
| | | | OR | OR | | | |
| | | | В | 4-7 hours post dose ^c | | | |

^a All post-dose windows are determined from the first dose of the visit (morning dose) and all PK samples must be collected before the second dose (PM dose).

^b Pre dose counts as both T0 and 12 hours post dose from previous evening (near trough). The previous evening's dose should be taken in the evening as late as possible, preferably before bedtime.

^c Post-dose sample collection can be +/- 15 minutes of the target time and must be at least 30 minutes from the previous sample (samples can be no closer than 30 minutes apart). The actual collection time must be recorded.

^d For the 3 to <7 year-old age range, two sampling timepoints are taken at each visit. The post-dose sample may be taken at either collection window A or collection window B. Ideally, it is better that the second sample is not taken at the same collection window at each visit. So, an attempt should be made to vary the collection time of the second sample as is feasible. For example, if on visit 5 the second sample is taken in collection window B, at visit 9 or 16, the second sample should ideally be taken in collection window A.

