8. PARTICIPANT POPULATION

Approximately 10 to 20 male and female participants between the ages of 3 and 17 years, inclusive, are planned to complete the study, balanced to the extent possible by age and the number of males and females.

The participants will be categorized by age in three groups: 13 to 17-year-olds (Group 1), 8 to 12-year-olds (Group 2), and 3 to 7-year-olds (Group 3). Enrollment will be balanced to the extent possible by sex and age with a minimum of 3 males and 3 females across all age groups, and a minimum of 3 participants in each age group.

Enrollment will proceed by age group according to the following process. Enrollment will commence first in the oldest age group (Group 1). After at least three participants in Group 1 have received two weeks of treatment at the starting dose, safety, and tolerability data will be reviewed by the DSMC. If tolerability and safety for those participants during that period is deemed acceptable, enrollment for Group 2 will proceed and dosing will commence at the starting dose. When at least three participants in Group 2 have received two weeks of treatment at the starting dose, safety and tolerability data will be reviewed by the DSMC. If tolerability and safety for Group 2 is deemed acceptable, enrollment for Group 3 will commence and dosing will begin at the starting dose. Participants in the younger age groups may be screened and enter the 4 to 6 week Screening period before DSMC review, but they will not be enrolled or dosed until the DSMC has reviewed and approved the initiation of dosing in the younger age group.

^{**} FDA Guidance on Conduct of Clinical Trials of Medical Products During the COVID-19 Public Health Emergency: Guidance for Industry, Investigators, and Institutional Review Boards (Center for Biologics Evaluation and Research; Center for Devices and Radiological Health; Center for Drug Evaluation and Research; Office of the Commissioner; Office of Clinical Policy and Programs; Office of Clinical Policy; Office of Good Clinical Practice) (2021).

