11.4 Pharmacokinetic Analysis

The PK analysis will be based on the endpoints listed in Section 6.3.1. Pharmacokinetic (PK) measures will be collected from all participants at Visits 5 (Week 2), 9 (Week 6), and 16 (Week 13, EOT).

NNZ-2591 PK concentrations will be listed by participant and time point for each dose level with actual time they were acquired. The concentrations will be summarized by time, dose level, and age group. For the concentrations measured at trough points dose relationship will be examined statistically with age group and/or body weight of participant as covariate.

Overall exposure parameters for NNZ-2591 such as C_{max} and AUC_{tau} may be derived by sparse non-compartmental analysis (NCA). Additionally, PK concentrations of NNZ-2591 measured in pediatric participants will be used to refine population PK model developed from adult NNZ-2591 PK data and extrapolated to pediatric population. After refinement, complete profiles for each participant will be simulated using range of variability of model parameters and individual covariate effects. A standard NCA approach will be used for simulated profiles to calculate parameters C_{max} , AUC_{tau} , etc. for characterization of NNZ-2591 exposure in pediatric participants.

The PK analysis details will be specified in the PK SAP.

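### In children under 7 the post-dose PK window varies within a child but is not balanced between children, so a dose level can end up with only early or only late samples

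*Protocol*

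**What the plan says.** Protocol section 4, Table 3, footnote d covers the youngest children: "For the 3 to <7 year-old age range, two sampling timepoints are taken at each visit". One is the pre-dose sample. For the other, "The post-dose sample may be taken at either collection window A or collection window B", that is, 1-3 h or 4-7 h after the morning dose. Footnote d then adds a preference: "Ideally, it is better that the second sample is not taken at the same collection window at each visit", followed by "So, an attempt should be made to vary the collection time of the second sample as is feasible". Its example has a child sampled in window B at Visit 5 and preferably in window A at one of the two later PK visits.

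Children aged 7 and over follow Table 2 and give a sample in both windows at every PK visit.

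The PK visits are Weeks 2, 6 and 13. Under Table 4 in section 7.2 these fall at 4, 8 and 12 mg/kg BID, one visit per dose level. Section 11.4 commits to a descriptive summary: "The concentrations will be summarized by time, dose level, and age group". The same section makes sparse NCA for Cmax and AUCtau optional. It commits to refining a population PK model, simulating full profiles for each participant and running standard NCA on those profiles.

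Section 8 requires "a minimum of 3 participants in each age group". The youngest enrolment group is ages 3 to 7, and no minimum is set for ages 3 to under 7. The SAP leaves PK to a separate plan.

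**The concern.** PK is part of the primary objective. A by-dose profile pooled across children is best supported when both post-dose windows are filled at each dose. Footnote d varies the window along the visit axis, which on the planned titration is the dose axis. It does not vary the window between children at the same visit. If all children under 7 follow the same compliant order, window and dose are completely confounded in this age range.

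An apparent departure from dose proportionality in the youngest children, or a difference from the older children, could then be partly an effect of when blood was drawn. The planned summary by time, dose level and age would also have empty cells for these children.

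**Working it through.** The documents state no sample size or precision for PK, so there is no figure of the plan's own to reproduce.

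**Step 1. Compliant window orders.** Over Visits 5, 9 and 16 there are 2^3 = 8 orders. Leaving out AAA and BBB, 6 contain both windows: AAB, ABA, ABB, BAA, BAB, BBA. If every child follows the same one, each dose level has one window. For example, BAA fits the protocol's own illustration and gives late-only samples at 4 mg/kg and early-only samples at 8 and 12 mg/kg. The gap is therefore possible under full compliance.

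**Step 2. How likely it is.** Assume n children under 7 each pick one of the 6 orders at random, independently. The documents do not say how windows are chosen, so this is an assumption.

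- One given level has a single window: 2(1/2)^n.
- Two given levels both do: 2(1/6)^n + 2(1/3)^n.
- All three do (all children share one order): 6(1/6)^n.

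By inclusion-exclusion, P(at least one level) = 6(1/2)^n - 6(1/6)^n - 6(1/3)^n + 6(1/6)^n = 6[(1/2)^n - (1/3)^n].

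| n | At least one level | All three levels |
|---|---|---|
| 2 | 6(0.2500 - 0.1111) = 83% | 1/6 = 16.7% |
| 3 | 6(0.1250 - 0.0370) = 53% | 1/36 = 2.8% |
| 4 | 6(0.0625 - 0.0123) = 30% | 1/216 = 0.5% |
| 5 | 6(0.0313 - 0.0041) = 16% | 1/1296 = 0.08% |

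Full enumeration of the orders gives the same values.

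**Step 3. What a single window does to sparse NCA.** Table 3, footnote b lets the pre-dose sample stand for both 0 and 12 h, so C(0) = C(12). The linear trapezoid over 0, t and 12 h then reduces to 6[C(0) + C(t)]. Half-life and absorption rate are not in the documents. I assumed a one-compartment oral model at steady state, half-life 2-8 h, ka 1-3 per h, and samples at 2 h (A) and 5.5 h (B).

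Worked case, half-life 4 h and ka 2 per h, unit dose and volume: C(0) = 0.156, C(2) = 0.865, C(5.5) = 0.482, true AUCtau = 1/0.1733 = 5.77. Early-only gives 6(0.156 + 0.865) = 6.13, ratio 1.06. Late-only gives 6(0.156 + 0.482) = 3.83, ratio 0.66.

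Ratios to the true value over the whole assumed range:

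| Windows at the level | AUCtau | Cmax |
|---|---|---|
| A only | 0.97-1.27 | 0.74-1.00 |
| B only | 0.39-0.86 | 0.22-0.82 |
| A and B | 0.87-0.98 | as A only |

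At identical true dose-normalised exposure, an early-only level would read from 0.97/0.86 = 1.1 times a late-only level (half-life 8 h, ka 1) to 1.23/0.39, a little over 3 times (half-life 2 h, ka 3).

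**Step 4. After balancing.** Alternating A-B-A and B-A-B gives one A and one B at every level with 2 children. With 3 children it gives 2A/1B, 1A/2B, 2A/1B, and with 4 it gives two of each at every level.

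**The case against.** A reader might infer that full compliance leaves these children with no usable sparse-NCA exposure at any dose. The documents do not support that. The pre-dose sample supplies two nominal points, so a single-window level still has three, and under the assumed kinetics an early-only level gives a usable though imprecise AUCtau. All three levels failing together is improbable if children choose independently. It becomes realistic mainly if sites share one habit or only one or two such children are enrolled.

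A reader might also argue that sites will prefer window A because the wait is shorter, which would raise the risk. If A is chosen 70% or 80% of the time independently at each visit, 3 children give 75% or 89% for at least one single-window level. The documents give no basis for that preference, and the protocol's example starts with B. Such a model also has 0.7^3 = 34% or 0.8^3 = 51% of children going A-A-A, which footnote d asks sites to avoid.

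The strongest counter-argument is that the committed route to exposure is the population model. It can use all doses and the recorded sampling times, and it does not need both windows at each dose. Protocol section 5.6 reports roughly dose-proportional adult PK, so dose-normalised pooling is plausible, and every varied order contains both windows. The protocol's age group is 3 to 7, and one fully sampled 7-year-old gives that group both windows at each dose reached. The PK SAP and Laboratory Manual were not available and could contain an allocation rule.

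These arguments stand and limit the point. They do not remove it. The by-dose summary is a commitment, a lone 7-year-old does not describe younger children, and proportionality seen in adults is something these data should help to test.

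**Conclusion.** The concern holds in a limited form. Footnote d varies the window across dose levels and leaves it unbalanced between children, so at least one dose level with a single post-dose window is likely when few children under 7 are enrolled: about 53% with 3, 30% with 4 and 16% with 5. All three levels are affected in about 3% of cases with 3 children. By-dose summaries and any sparse-NCA Cmax or AUCtau in this age range could then be biased, chiefly at late-only levels, or not comparable between doses or with older children.

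The probabilities assume independent random choice among compliant orders and participants on the planned dose at each visit. The bias ranges rest on assumed kinetics. The number of children under 7 is not fixed by the protocol. The point is minor. Confidence is moderate because the PK SAP and Laboratory Manual were not seen.

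**What to change.** In Table 3, replace the request to attempt variation with a window order assigned at enrolment and alternated across children under 7: A-B-A for the first, B-A-B for the second, and so on, at Visits 5, 9 and 16. Allow the other window when the assigned one is not feasible, and record the reason. Two children on the planned doses then cover both windows at every level. Dose adjustments under section 7.2.1 can break the link between visit and dose, so coverage should also be tallied by the dose actually taken.

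The cost is a line in Table 3 and a note in the visit kit. There are no extra blood draws, and families assigned window B wait longer at that visit.

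SAP section 2.2 says no participant was enrolled under protocol version 3.0, so a prospective change may come too late. If sampling is complete, report the number of A and B samples by dose level for children under 7, and state in the PK SAP and the study report that exposure in this age range rests on the population PK model.
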